7. STUDY ASSESSMENTS AND PROCEDURES

Study procedures and their timing are summarised in the Schedule of Assessments ([Appendix 5](#)). As protocol waivers or exemptions are not allowed, with the exception of immediate safety concerns, these should be discussed with the sponsor immediately upon occurrence or awareness to determine if the patient should continue or discontinue the study drug. Adherence to the study design requirements, including those specified in the Schedule of Assessments, is essential and required for study conduct.

All screening evaluations must be completed and reviewed to confirm that potential patients meet all eligibility criteria. The investigator will maintain a screening log to record details of all patients screened and to confirm eligibility or record reasons for screening failure ([Section 4.4.1](#)), as applicable. Procedures conducted as part of the patient's routine clinical management (e.g., blood count) and obtained before signing the ICF may be utilised for screening or baseline purposes provided the procedure met the protocol-specified criteria and was performed within the timeframe defined in the Schedule of Assessments.

Every effort should be made to ensure that protocol-required tests and procedures are completed. When a protocol-required test or procedure cannot be performed, the investigator will document the reason for this and any corrective and preventive actions the investigator has taken to ensure that normal processes are adhered to as soon as possible. The investigator will inform the study team of these incidents in a timely manner.

The maximum amount of blood collected from each patient over the duration of the study will not exceed 101.1 mL for the main study and additional 22 mL for the PK substudy. Repeat or unscheduled samples may be taken for safety reasons or for technical issues with the samples.

7.1. Efficacy Assessments

7.1.1. Test for COVID-19

Quantitative PCR to assess viral load on Day 1 before initiation of treatment and on Day 8 (± 1 day) (see Schedule of Assessments [[Appendix 5](#)]), will be performed by a central laboratory. Based on these assessments, changes in viral load from Day 1 to Day 8 will be calculated for each patient. The proportion of patients with undetectable SARS-CoV-2 on Day 8 will also be assessed.

Details regarding the collection, processing, storage, and shipment of oro-nasopharyngeal samples for qPCR testing will be provided to each investigational site before initiation of the study in the form of a laboratory manual. All oro-nasopharyngeal samples for qPCR must be processed and shipped as specified in the laboratory manual to maintain sample integrity. Any deviations from the processing steps (e.g., sample collection and processing steps, interim storage, or shipping conditions), including any actions taken, must be documented and reported to the sponsor. On a case-by-case basis, the sponsor may make a determination as to whether sample integrity has been compromised. Any deviation from the specified sample handling procedure that results in compromised sample integrity will be considered a protocol deviation.

Samples will be analysed using validated analytical methods, as approved by the sponsor.

7.1.2. Chest Imaging

Chest radiograph abnormalities will be detected by chest radiographs (X-ray) or chest CT scan on Day 1, 8 (± 1 day), and 31 (± 3 days); for each patient, the same assessment technique is to be used for each timepoint. Chest imaging performed within 48 hours of Day 1 is accepted and does not have to be repeated. Images will be reviewed for the presence of pulmonary infiltrates, pleural fluid, atelectasis, pulmonary oedema, and other findings.

7.1.3. Clinical and Functional Status

Clinical status (including the need for oxygen supplementation) will be assessed at least once a day, or whenever it changes, while hospitalised and on Days 8 (± 1 day), 15 (± 1 day), and 31 (± 3 days) using the 11-point WHO Clinical Progression Scale ([Appendix 13 – World Health Organization \(WHO\) Clinical Progression Scale](#)).

The pre-baseline (i.e., > 1 month prior to screening) functional status should be recorded, in addition to Day 1 prior to initiating study treatment, at hospital discharge, and on Days 8 (± 1 day), 15 (± 1 day), and 31 (± 3 days); functional status will be assessed by the Barthel index ([Appendix 7 – Barthel Index for Functional Assessment](#)).

7.1.4. Other Efficacy Assessments

The study day (from Day 1 to Day 31 (± 3 days)) on which the following events occurred will be recorded:

- Initiation of supplemental oxygen (of any type)
- Discontinuation of supplemental oxygen (of any type)
- Initiation of respiratory support
- Discontinuation of respiratory support
- Initiation of antivirals or immune-modulating drugs
- Discontinuation of antivirals or immune-modulating drugs
- ICU admission
- ICU discharge
- Hospital re-admission for COVID-19 signs or symptoms
- Hospital discharge
- Death

Additionally, the following information will be gathered for each patient on Days 4, 8 (± 1 day), 15 (± 1 day), and 31 (± 3 days) (yes/no):

- Receiving supplementary oxygen therapy
- Receiving high-flow oxygen
- Receiving non-invasive mechanical ventilation
- Receiving invasive mechanical ventilation or ECMO
- Requiring hospital admission related to COVID-19
- Requiring ICU admission
- Receiving subsequent antiviral therapies or immunomodulatory drugs

- Nosocomial infection
- Death

Based on these data, secondary endpoints for percentages of patients requiring oxygen therapy or different types of ventilation will be calculated and the time (in days) to sustained hospital discharge or withdrawal of supplemental oxygen therapy, percentages of patients with nosocomial infection or receiving subsequent antiviral or immunomodulatory therapies, hospitalisation in ICU, and hospitalisation will be measured.

Laboratory-based efficacy assessments that are to be performed during the study include:

- Proinflammatory biomarkers: (CRP, LDH, ferritin, IL-1 β , IL-6, IL-10, and TNF α) in each study arm from baseline (Day 1 prior to start of the study treatment) to Days 2, 3, 4, 8 (± 1 day), and 31 (± 3 days).
- Serological test (IgG) on Days 1 and 31 (± 3 days).

7.2. Safety and Tolerability Assessments

Safety will be assessed throughout the study through clinical and laboratory safety evaluations. These include medical history at screening, physical examinations, vital sign measurements, saturation of oxygen (SpO₂) by pulse oximetry (or arterial blood gas analyses [PaO₂]), and its respective FiO₂ ([Appendix 12 - Imputation of FiO₂ from oxygen flow values. High-flow oxygen therapy](#)), triplicate 12-lead ECGs, laboratory tests (haematology, coagulation, and chemistry), clinical AE monitoring, and verification of concomitant treatments.

7.2.1. Adverse Events

Adverse event definitions and assignment of severity and causality are detailed in [Appendix 1](#). All adverse events (AE) and adverse reactions (ARs), based on clinical signs and symptoms and laboratory measurements, will be measured daily until Day 31 (± 3 days), except treatment-related adverse events, treatment-emergent adverse events of special interest, and SAEs that will be measured daily until resolution or stabilisation to at least Grade 1, or to an acceptable level according to the investigator and the sponsor of his/her designated representative.

Adverse events will be elicited from the patient (or, when appropriate, from a caregiver, surrogate, or the patient's legally authorised representative) by the study site staff using a non-leading question such as "How are you feeling today?" or "Have you had any health concerns since your last visit?"

The investigator and any designees are responsible for detecting, documenting, and reporting events that meet the definition of an AE or SAE and remain responsible for following up AEs that are serious, considered related to the study treatment or the study, or that caused the patient to discontinue the study treatment (see [Section 4.4.2](#)).

Clinical Signs and Symptoms: AEs, including worsening of baseline signs and symptoms of disease observed by the investigator (preferably by the same physician for a same patient) or reported by patients to study nurses will be recorded and graded according to NCI-CTCAE version 5.0, accessible via internet

(http://ctep.cancer.gov/protocolDevelopment/electronic_applications/docs/CTCAE_v5_Quick_Reference_8.5x11.pdf). All events, including those considered not related to the study drugs, must be reported in the eCRF.

The following AEs will be considered and monitored as AEs of special interest: musculoskeletal disorders, CPK increases, and rhabdomyolysis; hypersensitivity reactions, cardiac events and transaminase elevations, and hepatobiliary disorders.

Laboratory Abnormalities: Laboratory abnormalities will be recorded and graded according to NCI-CTCAE version 5.0, accessible via internet (http://ctep.cancer.gov/protocolDevelopment/electronic_applications/docs/CTCAE_v5_Quick_Reference_8.5x11.pdf). Laboratory abnormalities that are of clinical significance will be recorded in Adverse Event eCRF.

Laboratory abnormalities for which NCI-CTCAE grading is not available will be classified as the fold below the lower limit of normal (<LLN) or fold above the ULN.

7.2.2. Reporting Serious Adverse Events

All the SAEs, regardless of the causality assessment, occurring after signing of ICF until Day 31 (± 3 days), will be reported. In addition, SAEs determined by the investigator to be related to the study drug, that have been identified after completion of the study will also be reported directly to the drug manufacturer as described below.

The SAEs occurring during the screening phase and after off-study will be reported using a paper “SAE form” that must be forwarded as mentioned below always within 24 hours to the Pharma Mar S.A. Pharmacovigilance Department by fax or email.

All SAEs, occurring from the date of initiating the study treatment (Day 1) until Day 31 (± 3 days) and regardless of study drug relationship, must be reported immediately, and always within 24 hours to the Pharma Mar S.A. Pharmacovigilance Department electronically by completing the applicable eCRF section. Only in situations of electronic system failure or pregnancy exposure during the clinical trial, the SAEs can be reported using paper on a SAE form by fax ([contact]) or email ([contact]). Out of office hours (Greenwich Meridian Time [GMT]), assistance on SAE reporting can be obtained by calling the Pharmacovigilance Department at [contact]. In case of electronic system failure or pregnancy exposure during the clinical trial, SAEs initially reported by alternative methods (not electronically), must be followed by a completed electronic SAE reporting on eCRF from the investigational staff within 1 working day.

All SAEs, regardless of the relationship with the study drug, must be followed until the event or its sequelae resolves or stabilises to at least Grade 1, or to an acceptable level according to the investigator and the sponsor or his/her designated representative.

7.2.3. Pregnancy

For female patients of child-bearing potential, a serum or urine pregnancy test, with sensitivity of at least 25 mIU/mL, and assayed in a certified laboratory, will be performed at screening.

Following a negative pregnancy test result at screening, appropriate contraception must be commenced before the patient may receive study drugs.

Additional pregnancy tests will be performed whenever 1 menstrual cycle is missed or when potential pregnancy is otherwise suspected. In the case of a positive confirmed pregnancy, the patient will be withdrawn immediately from administration of study drugs, but may remain in the study for safety and efficacy follow-up.

Fertile male patients and female patients who are of child-bearing potential, who are, in the opinion of the investigator, sexually active and at risk of pregnancy with their partner(s), will need to affirm that they meet the criteria for use of highly effective contraception methods throughout the study and for at least 6 months after the last dose of plitidepsin. Patients in the control arm must use effective contraception during the time indicated in the approved product information (SmPC or leaflet). If no information is available in the approved product information, patients in the control arm must use effective contraception for at least one week after the study completion or the time indicated based on the investigator's discretion. The investigator, or designated subinvestigator, will discuss with the patient the need to use effective contraception methods consistently and correctly and document such conversation in the patient's chart. In addition, the investigator will instruct the patient to call immediately if contraception methods are discontinued or if pregnancy is known or suspected in the patient or the patient's partner.

7.2.4. Clinical Laboratory Evaluations

Blood samples for laboratory safety assessments, including haematology (RBC, haemoglobin, haematocrit, WBC with differential, platelet count), coagulation (D-dimer), serum chemistry (ALT, AST, alkaline phosphatase, GGT, lactate dehydrogenase [LDH], total bilirubin, direct bilirubin, glucose [fasting], sodium, potassium, calcium (albumin adjusted calculation), magnesium, BUN, creatinine, calculated creatine clearance [Cockcroft-Gault equation], CPK, albumin, amylase, lipase, procalcitonin, troponin [troponin I or T according to local practice for screening and troponin T [high sensitivity] by central laboratory for on-study tests], and N-terminal pro-B-type natriuretic peptide [NT-pro-BNP], serological SARS-CoV-2 testing (immunoglobulin [Ig]G), and immunology (CRP, ferritin, IL-1 β , IL-6, IL-10, TNF α) will be drawn at the timepoints described in the Schedule of Assessments ([Appendix 5](#)). Testing to be performed by local laboratory at screening and by central laboratory for on-study tests at Day 1 prior to initiation of study treatment, once daily during hospitalisation, and at follow-up visits on Days 8 (\pm 1 day) and 31 (\pm 3 days), except, troponin T (high sensitivity), and NT-pro-BNP that will be measured on Day 1, Day 8 (\pm 1 day), and Day 31 (\pm 3 days). Tests performed within 24 hours of screening do not have to be repeated.

Details regarding the collection, processing, storage and shipment of blood samples for laboratory safety assessments will be provided to each investigational site before initiation of the study in the form of a laboratory manual. All blood samples must be processed and shipped as specified in the laboratory manual to maintain sample integrity. Any deviations from the processing steps (e.g., sample collection and processing steps, interim storage or shipping conditions), including any actions taken, must be documented and reported to the sponsor. On a case-by-case basis, the sponsor may make a determination as to whether sample integrity has

been compromised. Any deviation from the specified sample handling procedure that results in compromised sample integrity will be considered a protocol deviation.

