- Vital signs: temperature, sitting blood pressure, heart rate, respiratory rate, PaO₂ (obtained either by arterial blood gas analyses or from saturation of oxygen (SpO₂) by pulse oximetry), and its respective FiO₂ ([Appendix 12 - Imputation of FiO₂ from oxygen flow values. High-flow oxygen therapy](#)) to be measured at screening, on Days 1 to 3 just before start and end of each plitidepsin infusion (plitidepsin groups)/once daily on Days 1 to 3 (control group), further once daily while the patient is hospitalised, and on Days 8 (± 1 day) and 31 (± 3 days). To estimate the PaO₂/FiO₂ ratio, the required equation would be used for imputing PaO₂ from SpO₂ ([Appendix 9 – Imputation of PaO₂ from SpO₂](#)), and the information on the oxygen delivery devices and oxygen flow prescribed would be utilised for imputation of FiO₂.
- Physical examination will be performed at Day 1 prior to initiation of study treatment, once daily during hospitalisation, and at follow-up visits on Days 8 (± 1 day) and 31 (± 3 days).
- Electrocardiogram: QTcF prolongation will be assessed at screening and on Days 1, 3 (postinfusion), and 31 (± 3 days), and any QTcF values >500 msec will be flagged as increasing the likelihood of the treatment being proarrhythmic (per ICH Guidance E14).
- Haematology* ([Appendix 2- Clinical Laboratory Evaluations](#)): red blood cells (RBC), haemoglobin, haematocrit, white blood cells (WBC) with differential and platelet count will be measured at Day 1 prior to initiation of study treatment, once daily during hospitalisation, and at follow-up visits on Days 8 (± 1 day) and 31 (± 3 days). Testing to be performed by the local laboratory for screening and by central laboratory for on-study tests (tests performed within 24 hours of screening do not have to be repeated).
- Serum chemistry* ([Appendix 2- Clinical Laboratory Evaluations](#)): it will be performed at Day 1 prior to initiation of study treatment, once daily during hospitalisation, and at follow-up visits on Days 8 (± 1 day) and 31 (± 3 days), except, troponin T (high sensitivity), and NT-pro-BNP that will be measured on Day 1, 8 (± 1 day) and 31 (± 3 days). Tests performed within 24 hours of screening do not have to be repeated.

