ideally completed 20 to 30 minutes before plitidepsin infusion start and, exceptionally, up to 2 h pre-infusion of plitidepsin) followed by a 60-minute infusion of plitidepsin. A 30 (± 5) minute window is allowed for the plitidepsin administration between each day, and plitidepsin should not be given earlier than 23.5 hours on Days 2 and 3 of previous day plitidepsin administration.

- Administration of remdesivir 200 mg IV on Day 1, followed by 100 mg/day IV on Days 2 to 5 (*per physician decision for patients randomised to control arm*). Administration of favipiravir 1600 mg BID PO on Day 1, followed by 600 mg BID PO daily for 2 to 5 days (*per physician decision for patients randomised to control arm*). Administration of any other regulatory-approved antiviral treatment to follow approved SmPC.

7.4.2.2. Days 5, 6, and 7

The following assessments will be completed on Days 5, 6, and 7 (or until discharged) unless otherwise stated:

- Vital signs (temperature, blood pressure, heart rate, respiratory rate) and PaO₂ (obtained either by arterial blood gas analyses or from saturation of oxygen (SpO₂) by pulse oximetry, and its respective FiO₂ once daily while hospitalised).
- Concomitant medications.
- Adverse events/TEAEs.
- Clinical status, using the 11-point WHO Clinical Progression Scale (highest category that applies) ([Appendix 13](#)):

For patients who remain hospitalised after Day 7, the above assessments should be performed once each day until discharge.

Additionally, administration of dexamethasone base will be continued at 6 mg/day PO/IV (equivalent to 7.2 mg dexamethasone phosphate), per physician judgement based on patient clinical condition and evolution. Administration of remdesivir 100 mg/day IV or favipiravir 600 mg BID PO daily may continue until Day 5 per physician's decision for patients randomised to control arm. Administration of any other regulatory-approved antiviral treatment to follow approved SmPC.

7.4.2.3. Days 8 and 31

The following assessments will be performed on Days 8 (± 1 day), 31 (± 3 days), and study discontinuation unless otherwise stated:

- IWRS registration (*Day 31 and at end of study visit*).
- Vital signs (temperature, blood pressure, heart rate, respiratory rate) and PaO₂ (obtained either by arterial blood gas analyses or from saturation of oxygen (SpO₂) by pulse oximetry, and its respective FiO₂).
- Physical examination.

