8.7. Safety Analysis

Safety analyses will be based on the As Treated Population. All safety parameters will be summarised and also listed by patient.

Treatment-emergent Adverse Events: The verbatim terms used in the eCRF by investigators to identify TEAEs will be coded using the Medical Dictionary for Regulatory Activities (MedDRA) and will be graded according to NCI CTCAE version 5.0. All reported AEs that occur or worsen on or after the first dose of study drug (Day 1) up through Day 31 (± 3 days) (last protocol-specified follow-up visit) will be included in the analysis. Treatment-emergent AEs will be summarised by MedDRA system organ class and preferred term. For each TEAE, the percentage of subjects who experience at least 1 occurrence of the TEAE will be summarised overall and by treatment group. The SAEs, AEs of special interest, and deaths will be listed. All TEAEs resulting in discontinuation of study treatment, dose modification, dose interruption, or a delay in treatment with the study drug will be listed and summarised by system organ class/preferred term.

Clinical Laboratory Tests: Laboratory data will be summarised by type of laboratory test. The worst toxicity grade will be tabulated. Parameters with predefined NCI CTCAE version 5.0 toxicity grades will be summarised. Change from baseline to the worst TEAE grade experienced by the subject during the study will be provided as shift tables.

Electrocardiograms: The effects of treatment on QTcF interval, including events of QTcF >500 msec and >60 msec from baseline, will be evaluated by means of descriptive statistics and frequency tabulations.

Subgroup analysis of TEAEs and clinically relevant laboratory tests will be performed based on prognostic factors of medical interest (e.g., sex, age, administration of remdesivir/favipiravir in the control arm, etc.).

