- 3 Vital signs:** Temperature, sitting blood pressure, heart rate, respiratory rate, PaO₂ (obtained either by arterial blood gas analyses or from saturation of oxygen (SpO₂) by pulse oximetry), and its respective FiO₂ ([Appendix 12 - Imputation of FiO₂ from oxygen flow values. High-flow oxygen therapy](#)) to be measured at screening, on Days 1 to 3 just before start and end of each plitidepsin infusion (plitidepsin groups)/once daily on Days 1 to 3 (control group), further once daily while the patient is hospitalised, and on Days 8 and 31 (± 3 days). To estimate the PaO₂/FiO₂ ratio, the required equation would be used for imputing PaO₂ from SpO₂ ([Appendix 9 – Imputation of PaO₂ from SpO₂](#)), and the information on the oxygen delivery devices and oxygen flow prescribed would be utilised for imputation of FiO₂.
- 4 ECG:** QTcF prolongation to be assessed at screening and on Days 1, 3 (postinfusion), and 31 (± 3 days), and any QTcF values >500 msec will be flagged as increasing the likelihood of the treatment being proarrhythmic (per ICH Guidance E14).
- 5 Haematology:** RBC, haemoglobin, haematocrit, WBC with differential, platelet count. Testing to be performed by the local laboratory for screening and by central laboratory for on-study tests (tests performed within 24 hours of screening do not have to be repeated)
- 6 Serum chemistry:** *Prestudy screening assessments:* ALT, AST, total bilirubin, sodium, potassium, calcium (albumin adjusted), magnesium, creatinine, calculated creatinine clearance (Cockcroft-Gault equation), CPK, and troponin (I or T according to local practice). *On study assessments:* ALT, AST, alkaline phosphatase, GGT, LDH, total bilirubin, direct bilirubin, glucose (fasting), sodium, potassium, calcium (albumin adjusted calculation), magnesium, blood urea nitrogen, creatinine, calculated creatinine clearance (Cockcroft-Gault equation), CPK, albumin, amylase, lipase, procalcitonin, troponin T (high sensitivity), and NT-pro-BNP. Note that testing to be performed by the local laboratory for screening and by central laboratory for on-study tests; tests performed within 24 hours of screening do not have to be repeated. All serum chemistry parameters will be measured at Day 1 prior to initiation of study treatment, once daily during hospitalisation, and at follow-up visits on Days 8 (± 1 day) and 31 (± 3 days); except, troponin T (high sensitivity), and NT-pro-BNP that will be measured on Day 1, Days 8 (± 1 day) and 31 (± 3 days).

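### The protocol gives two incompatible schedules for in-hospital safety laboratory tests; if the daily one is followed, or sites differ, the worst-grade tables depend on length of stay

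*Protocol*

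**What the plan says.** Three places in the protocol call for daily tests in hospital.

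- Section 7.2.4 has central-laboratory testing "for on-study tests at Day 1 prior to initiation of study treatment, once daily during hospitalisation, and at follow-up visits on Days 8" and 31. Troponin T and NT-pro-BNP are excepted.
- The synopsis (Evaluation) says of haematology that it "will be measured at Day 1 prior to initiation of study treatment, once daily during hospitalisation, and at follow-up visits on Days 8" and 31, and words serum chemistry alike.
- Appendix 5, Table 5, footnote 6 (serum chemistry only): "All serum chemistry parameters will be measured at Day 1 prior to initiation of study treatment, once daily during hospitalisation". The haematology footnote (5) has no daily rule.

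Two places do not.

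- Section 7.4.2.2 opens with "The following assessments will be completed on Days 5, 6, and 7 (or until discharged) unless otherwise stated" and then lists vital signs with oxygenation, concomitant medications, adverse events and clinical status. It contains no laboratory test. It continues: "For patients who remain hospitalised after Day 7, the above assessments should be performed once each day until discharge".
- The haematology and serum chemistry rows of Table 5 are marked at screening and on Days 1-4, 8 and 31. They are blank on Days 5, 6, 7, 9, 10 and 15.

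Section 7.2.4 also says that samples "will be drawn at the timepoints described in the Schedule of Assessments", so it sends the reader to a grid that does not show its own daily rule.

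On analysis, Section 8.7 says of laboratory data: "The worst toxicity grade will be tabulated". It adds shift tables from baseline to the worst grade during the study.

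**The concern.** Section 7 makes adherence to the Schedule of Assessments mandatory, yet that schedule disagrees with itself and with the body text. A site reading Section 7.2.4 or footnote 6 draws chemistry every day until discharge. A site reading Section 7.4.2.2 or the Table 5 cells makes no routine draw between Day 4 and the Day 8 visit, and none between Day 8 and Day 31. CPK increases and transaminase elevations are adverse events of special interest, so this decides how closely the main laboratory signals are watched just after dosing on Days 1-3.

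The analysis consequence is conditional. A patient's worst grade is a maximum over that patient's draws, and a maximum tends to rise with their number. Under the daily rule, draws stop at discharge apart from Days 8 and 31, and time to sustained discharge is the key secondary endpoint. If one arm goes home earlier, it is sampled less and may show a milder worst-grade profile with no true difference in toxicity.

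**Working it through.** The protocol states no figure for this point, so there is none to reproduce. The check counts scheduled draws and then illustrates the effect on a worst-grade table.

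**Step 1. Scheduled post-baseline laboratory days, by discharge day L.**

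- Grid reading (Section 7.4.2.2 and the Table 5 cells): Days 2, 3, 4, 8 and 31, which is 5 for everyone. The minimum stay of 4 days (Section 3.1) covers Days 2-4.
- Daily reading (Section 7.2.4, synopsis, footnote 6): Days 2 to L, plus Days 8 and 31 where not already counted. This gives (L − 1) + 2 = L + 1 draws for L of 4 to 7, and (L − 1) + 1 = L draws for L of 8 to 30.

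| Discharge day | Grid | Daily |
|---|---|---|
| 4 | 5 | 5 |
| 6 | 5 | 7 |
| 8 | 5 | 8 |
| 10 | 5 | 10 |
| 15 | 5 | 15 |
| 20 | 5 | 20 |

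This step needs no assumption about the drug.

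**Step 2. Worst-grade illustration, no true difference.** Assumptions, none of them given in the protocol for this purpose:

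- Stay is exponential with medians of 8 and 5.7 days, at least 4 days, capped at Day 31. These medians are the design values for oxygen withdrawal (Section 8.1; 8/1.4 = 5.71), borrowed here for discharge.
- Each draw has the same chance p of showing the grade of interest, independently of the others and in both arms.
- P(at least one) = mean of 1 − (1 − p)^draws.

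Mean draws under the daily reading are 12.1 (longer stay) v 9.7 (shorter stay).

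| p per draw | Longer stay | Shorter stay | Ratio | Grid, both arms: 1 − (1 − p)^5 |
|---|---|---|---|---|
| 1% | 11.1% | 9.1% | 9.1/11.1 = 0.82 | 4.9% |
| 2% | 20.6% | 17.2% | 17.2/20.6 = 0.83 | 9.6% |
| 5% | 42.0% | 36.4% | 36.4/42.0 = 0.87 | 22.6% |

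Adding 2 days to every stay gives 13.4 v 11.0 draws and the same direction.

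**Step 3. Sensitivity to timing and persistence.** Independent draws with constant risk to Day 31 are an unfavourable case. The same stay model (longer-stay median 6 to 12 days, ratio 1.4) was run with one abnormality per patient, with uniform onset over a window and lasting several days. It counts as detected if any draw falls within it.

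| Onset window | Duration | Ratio, shorter v longer stay |
|---|---|---|
| Days 2-8 | 5 days or more | 1.00 |
| Days 2-10 | 3-10 days | 0.95-0.98 |
| Days 2-31 | 3-10 days | 0.86-0.94 |

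Persistent early abnormalities are caught in both arms, mostly by the shared draws on Days 2-4 and 8. The gap is material only for late or short-lived abnormalities.

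**The case against.** The strongest reply is that the analysis part belongs to the statistical analysis plan. Section 8 defers specifics to it, Section 8.7 is descriptive with no between-arm laboratory test, and a worst-grade summary over all data is common practice. This stands against calling the Section 8.7 tables wrong. It does not reach the schedule conflict, because a SAP cannot repair what sites did or did not collect.

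Four stronger inferences are tempting, and the protocol does not support them.

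- *Plitidepsin is made to look safer by construction.* This needs the daily rule to be followed, or sites to differ, and plitidepsin to shorten stay. Under the Table 5 grid every patient has the same scheduled days. Ratios of 0.82 to 0.87 also rest on a borrowed effect and on independent draws, so they are an upper-end illustration.
- *Table 5 omits daily tests.* Its footnote 6 states them for chemistry. The conflict lies within the table as well as between it and the text.
- *Under the grid nothing is sampled between Day 4 and Day 8.* Only routine draws are missing. Section 7 allows unscheduled safety samples, Appendix 1 asks for re-tests at least every 72 hours after treatment-related Grade 3 or higher events, and Day 8 has a window of 1 day either way.
- *Vital signs have the same fault.* Measurement on Days 1-3 does differ by arm, but Section 8.7 plans no worst-value vital-sign table, so the argument does not carry over.

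It is also fair to object that confining the comparison to the common days would take many in-hospital results on events of special interest out of it. In the 2% example, 17.2% and 20.6% would become 9.6% in each arm. That rules out replacing the all-data table, but not adding a second one.

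The words allowing for exceptions at the head of Section 7.4.2.2 do not settle the matter: they qualify the listed assessments and add none. Nor does the 101.1 mL blood ceiling in Section 7, since no volume per draw is given for the main study.

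**Conclusion.** The inconsistency is certain and rests on the text alone. Section 7.2.4, the synopsis and, for chemistry, footnote 6 require daily tests in hospital; Section 7.4.2.2 and the Table 5 cells do not. The difference is 5 draws against 10 for a Day 10 discharge and 5 against 20 for a Day 20 discharge.

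The effect on the worst-grade and shift tables is conditional on the daily rule being followed or on sites differing. Its direction then favours the arm discharged earlier. Its size cannot be fixed from the protocol: the ratio runs from about 0.82 with independent draws at constant risk to 1.00 for early abnormalities lasting 5 days or more. These figures depend on assumed stays and on assumed timing and persistence. The point is worth correcting because it changes what is collected on events of special interest and costs little.

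**What to change.** Make the synopsis, Section 7.2.4, Section 7.4.2.2, the Table 5 cells and footnote 6 state one laboratory schedule, and align the haematology footnote with it. Which schedule to keep is the sponsor's decision.

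If any sampling that depends on length of stay remains, including data already collected under differing site practice, keep the all-data worst-grade and shift tables of Section 8.7. Add a between-arm version restricted to the days scheduled for every patient under either reading: Days 1-4, 8 and 31, with Day 1 as baseline. Reading the two together shows whether a difference reflects toxicity or sampling.

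The cost is protocol wording and one extra set of tables. No result leaves the all-data comparison.
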